4.3 STRATEGIES FOR RECRUITMENT AND RETENTION

- Participants will be compensated by receiving \$5 cash for each visit
- Subjects will receive an email, text or phone call reminder for all their scheduled visits according to their preference
- The source of the subjects will be those who visited Siperstein Dermatology Group and allowed their information to be used in order to be contacted for promotions and trials.

4.4 PARTICIPANT WITHDRAWAL ORTERMINATION

4.4.1 REASONS FOR WITHDRAWAL OR TERMINATION

Participants are free to withdraw from participation in the study at any time.

An investigator may terminate participation in the study if:

- The participant's health declines
- The participant needs any surgery or other serious medical interventions
- The participant meets an exclusion criterion (either newly developed or not previously recognized) that precludes further study participation.
- The participant fails to show up for follow-up and final visits

The primary investigator will attempt to visit all participants that have withdrawn or terminated from the trial if they are unable to make their follow-up visits to ensure as much data as possible has been collected and that all safety parameters have been met.

4.5 PREMATURE TERMINATION OR SUSPENSION OF STUDY

This study may be temporarily suspended or prematurely terminated if there is sufficient reasonable cause. If the study is prematurely terminated or suspended, the primary investigator will promptly inform the IRB as well as provide the reason(s) for the termination or suspension.

Circumstances that may warrant termination or suspension include, but are not limited to:

- Determination of unexpected, significant, or unacceptable risk to participants
- Insufficient compliance to protocol requirements

Study may resume once concerns about safety, protocol compliance, or data quality is addressed.

5 STUDY AGENT

5.1 STUDY EQUIPMENT

5.1.1 DEVICES FOR INTERVENTION

Sciton's BBL, Joule Platform

5.1.2 DEVICE INDICATION

The Sciton BBL as described in the 510(k) summary for the Joule multi-platform system on which it is located, is described as a laser surgical instrument for use in general and plastic surgery and in dermatology. One of the intended uses is described as the treatment of vascular lesions. We are therefore using this device as per indication since a vascular lesion is a lesion relating to, affecting, or consisting of a vessel or vessels, especially those that carry blood and purpura is a lesion relating to the injury of blood vessels in which blood escapes into the surrounding skin. We will mainly be using the 560 and 590 cut off filters since these are the recommended filters to treat vascular lesions.

5.1.2 DURATION OF THERAPY

- The BBL treatment will take approximately 15 minutes
- The last treatment will be done on Day 21

5.1.3 OTHER EQUIPMENT NECCESARY

- Metal Goggles for participants and IPL specific wavelength goggles for investigator
- Punch Biopsy Kit

6 STUDY PROCEDURES AND SCHEDULE

6.1 STUDY PROCEDURES/EVALUATIONS

6.1.1 STUDY SPECIFIC PROCEDURES

- Medical history obtained and verbally verified
- Assigned arm meeting inclusion criteria is shaved to remove all hair
- Digital Pictures taken of bilateral hands and arms
- Counseling the subjects on the treatment that they will be receiving and post-care instructions.
- The study coordinator will check before the patient leaves that all appropriate photos and paperwork have been completed.
- BBL study treatment will be done according the protocol below outlining specific settings

BBL Only Protocol

1st Treatment Settings

- 1. SkinTyte Filter ST: 150 Joules, 15msec, 15 degrees for 10 continuous passes in alternating directions (5 each direction)
- 2. 590 Filter: 8J, 15msec, 15 degrees x 2 passes
- 3. 590 Filter: 10J 15msec, 15 degrees x 2 passes
- 4. 560 Filter: 8J, 15msec, 15 degrees x 2 passes

2nd Treatment Settings

If any answers on the post procedure side effects questionnaire from day 0,1, or 2 were SEVERE or if the patient had blisters from the previous treatment

Decrease Step 3 & 4 by 2 Joules

1. SkinTyte Filter ST: 150 Joules, 15msec, 15 degrees for 10 continuous passes in alternating directions

- 2. 590 Filter: 8J, 15msec, 15 degrees x 2 passes
- 3. 590 Filter: 8J 15msec, 15 degrees x 2 passes
- 4. 560 Filter: 6J, 15msec, 15 degrees x 2 passes

If any answers on the post procedure side effects questionnaire on day 0,1, or 2 were MODERATE with NO blistering

Decrease Step 3 & 4 by 1 Joule

- 1. SkinTyte Filter ST: 150 Joules, 15msec, 15 degrees for 10 continuous passes in alternating directions
- 2. 590 Filter: 8J, 15msec, 15 degrees x 2 passes
- 3. 590 Filter: 9J 15msec, 15 degrees x 2 passes
- 4. 560 Filter: 7J, 15msec, 15 degrees x 2 passes

If all answers on the post procedure side effects questionnaire on day 0,1, or 2 protocol were MINIMAL

Keep Settings the same as previous visit

- 1. SkinTyte Filter ST: 150 Joules, 15msec, 15 degrees for 10 continuous passes in alternating directions (5 each direction)
- 2. 590 Filter: 8J, 15msec, 15 degrees x 2 passes
- 3. 590 Filter: 10J 15msec, 15 degrees x 2 passes
- 4. 560 Filter: 8J, 15msec, 15 degrees x 2 passes

If all answers on the post procedure side effects questionnaire on day 0,1, or 2 protocol were NONE

Increase Step 1 by 10 additional passes and Increase Step 3 & 4 by 1 Joule

- 1. SkinTyte Filter ST: 150 Joules, 15msec, 15 degrees for 20 continuous passes in alternating directions (10 each direction)
- 2. 590 Filter: 8J, 15msec, 15 degrees x 2 passes
- 3. 590 Filter: 11J 15msec, 15 degrees x 2 passes
- 4. 560 Filter: 9J, 15msec, 15 degrees x 2 passes

3rd and 4th Treatment Settings

-If any answers on the post procedure side effect questionnaire were SEVERE or if the patient had blisters from the previous treatment

Decrease Step 3 & 4 by 2 Joules from settings at previous visit

-If any answers on the post procedure side effect questionnaire were MODERATE with NO blistering

Decrease Step 3 & 4 by 1 Joule from settings at previous visit

-If any answers on the post procedure side effect questionnaire were MINIMAL with NO blistering

Keep Settings the same as previous visit

-If all answers on the post procedure side effect questionnaire were NONE

Increase Step 1 by 10 additional passes and Increase Step 3 & 4 by 1 Joule from settings at previous visit

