2.3 POTENTIAL RISKS AND BENEFITS

2.3.1 KNOWN POTENTIAL RISKS

Common potential risks of BBL include swelling, pain, scabbing, blistering, reduction of hair and lentigenes, erythema, pruritus, lightening and darkening of the skin, and reactivation of herpes infection. Rare but potential risks of BBL include severe burn, skin ulceration, scarring and infection.

Common potential risks of a skin biopsy include bleeding and scarring while rare but potential risks include infection and allergy to the lidocaine, bandages, or sutures used in the procedure.

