3 STUDY DESIGN, OBJECTIVES, AND ENDPOINTS

3.1 DESCRIPTION OF THE STUDY DESIGN

- A Prospective, Randomized, Split-Arm Clinical Study
- Single Center
- Study agent: Sciton's BBL
- Study Interventions: BBL Treatment on Day 0, Day 7, and Day 21
- Evaluations on Day 0, Day 7, Day 14, Day 21, Day 22, Day 51.

This will be a prospective, split-arm clinical study in which 5 subjects will be randomized to which arm will be treated with Sciton's BBL.

All subjects will have their arms shaved prior to the procedure and cleaned thoroughly with alcohol. After the procedure a zinc-based sunscreen will be applied to both arms.

Before each of the four treatments and 30 days after the last treatment, the subjects' number and square area of ecchymoses will be measured by an evaluator. Side effects will be measured on Day 0, 1, 2, 7, 14, 21, 22 and 51. Digital photography of subject's arms will be done on day 0, 7, 14, 21, and 51.

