6.2.2 ENROLLMENT/BASELINE

Enrollment/Baseline Visit (Visit 1, Day 0) Treatment #1

- Review in depth the study design with subjects and obtain informed consent of potential participants verified by signature
- Perform examination and verbally review subject's medications, medical history, and subject questionnaire to determine eligibility based on inclusion/exclusion criteria

- Obtain demographic information
- Shave the hair on the subjects' lower arms
- Take digital pictures of subjects' lower arms
- Have evaluator measure the size and number of bruises and skin tears
- Perform the BBL treatment on assigned arm per protocol
- Record adverse events as reported by participant or observed by investigator
- Perform protocol adherence check by study coordinator
- Expected post-procedure side effects and possible emergent situations reviewed with subjects and post-op written instructions given

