6.2.3 FOLLOW UP TREATMENTS

2nd Treatment (Visit 2, Day 7 +/- 2 days)

- Record adverse events as reported by participant or observed by investigator.
- Subjects fill out adherence questionnaire and evaluator review to ensure continued eligibility
- Evaluator measures the size and number of bruises and number of skin tears
- Shave bilateral lower arms
- Take digital pictures of subjects' lower arms
- Perform the BBL treatment the second time per protocol
- Record adverse events as reported by participant or observed by investigator.
- Perform protocol adherence check by study coordinator
- Expected post-procedure side and post-op written instructions reviewed

3rd Treatment (Visit 3, Day 14 +/-2 days)

- Record adverse events as reported by participant or observed by investigator.
- Subjects fill out adherence questionnaire and evaluator review to ensure continued eligibility
- Evaluator measures the size and number of bruises and number of skin tears
- Shave bilateral lower arms
- Take digital pictures of subjects' lower arms
- Perform the BBL treatment a third time per protocol
- Record adverse events as reported by participant or observed by investigator
- Perform protocol adherence check by study coordinator
- Expected post-procedure side and post-op written instructions reviewed

4th Treatment (Visit 4, Day 21 +/-2 days)

- Record adverse events as reported by participant or observed by investigator.
- Subjects fill out adherence questionnaire and evaluator review to ensure continued eligibility
- Evaluator measures the size and number of bruises and number of skin tears
- Shave bilateral lower arms
- Take digital pictures of subjects' lower arms
- Perform a BBL treatment on the assigned arm a fourth time per protocol
- Record adverse events as reported by participant or observed by investigator.
- Perform protocol adherence check by study coordinator

Expected post-procedure side and post-op written instructions reviewed

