6.2.5 FINAL STUDY VISIT

Follow-up Visit 2 (Visit 6, Day 51 +/-2 days)

- Record adverse events as reported by participant or observed by investigator.
- Subjects fill out adherence questionnaire and evaluator review to ensure continued eligibility
- Evaluator measures the size and number of bruises and number of skin tears
- Shave bilateral lower arms
- Take digital pictures of subjects' lower arms
- Provide final instructions

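### Section 6.1.1 shaves only the assigned arm where every other section shaves both, and the evaluator's measurement is listed after shaving at Day 0 but before it at Day 51

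*Combined protocol and SAP*

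**What the plan says.** **Which arm is shaved.** Section 6.1.1 has: "Assigned arm meeting inclusion criteria is shaved to remove all hair". Its next bullet is "Digital Pictures taken of bilateral hands and arms". Section 3.1 says "All subjects will have their arms shaved prior to the procedure and cleaned thoroughly with alcohol". Section 6.2.2 (Day 0) says "Shave the hair on the subjects' lower arms". Section 6.2.3 (Days 7, 14 and 21) says "Shave bilateral lower arms", and section 6.2.5 (Day 51) uses the same words.

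**When the evaluator measures.** At Day 0 the bullet "Have evaluator measure the size and number of bruises and skin tears" comes after the shaving and picture bullets. At Day 51 the bullet "Evaluator measures the size and number of bruises and number of skin tears" comes before them, and the lists for Days 7, 14 and 21 follow the Day 51 pattern.

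**What depends on it.** Section 3.2.2 defines the primary endpoint as the between-arm difference in change, for lesion area and for lesion number, with Day 0 and Day 51 as the two ends. Section 3.1 gives the counting and sizing to an evaluator at the visits. Section 8.5 masks picture evaluators to side and restricts knowledge of the assignment to the treating investigator and the coordinator.

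**Hair.** Section 2.3.1 includes among the common risks of BBL "blistering, reduction of hair and lentigenes, erythema".

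**The concern.** Each subject's untreated arm is the only control, and counting and sizing bruises takes judgement. Two protections therefore matter: the evaluator should have no avoidable cue to the treated side, and both arms should be measured in the same state at both ends of the change.

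The one-arm instruction in 6.1.1 threatens the first. A shaved arm beside an unshaved one is an obvious marker, and the masking in 8.5 cannot work if preparation of the arm displays the assignment.

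The reversed order threatens the second. As listed, baseline is read on freshly shaved skin and the final value on regrown skin. If hair affects how lesions are seen, the two readings are not like for like. If BBL thins the hair, the arms may also differ from each other at Day 51, which is the difference that the primary endpoint would pick up.

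**Working it through.** **Step 1. The shaving instructions side by side.** Both arms: 3.1, 6.2.2, three visits in 6.2.3, and 6.2.5, which makes six statements. Assigned arm only: 6.1.1, one statement. They cannot all be followed.

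**Step 2. The listed order at each measurement visit.**

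| Visit | Listed order | Skin when the evaluator measures |
|---|---|---|
| Day 0 (6.2.2) | shave, pictures, measure | freshly shaved |
| Days 7, 14, 21 (6.2.3) | measure, shave, pictures | regrown since the previous visit |
| Day 51 (6.2.5) | measure, shave, pictures | regrown since Day 21 |

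Section 6.2.4 (Day 22) lists no shaving, so regrowth at Day 51 is 51 − 21 = 30 days. With the ±2-day window at each visit it is 26 to 34 days. Pictures follow shaving in every row.

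**Step 3. What this could do to the primary contrast.** The plan gives no sample-size, power or variability figure (8.4 is marked not applicable for a pilot), so there is nothing to reproduce. The following is an illustration only.

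Let a fraction v of lesions be seen: v = 1 on shaved skin and v = q on unshaved skin. Let B be the true count per arm at Day 0, and A_T and A_C the true Day 51 counts on the treated and control arms. Subscripts 0 and 1 mark Day 0 and Day 51. The apparent treated-minus-control difference in change is

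D = (v1T × A_T − v0T × B) − (v1C × A_C − v0C × B).

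Assumptions: q = 0.95, 0.90 or 0.80; B = 15, borrowed from the small growth-factor study described in the background (section 2.1) and not a planning value of this trial. Under no effect A_T = A_C = 15. Under an assumed 50% reduction A_T = 7.5 and A_C = 15.

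- **Same shaved state at both visits, both arms.** No effect: D = 0. 50% effect: D = 7.5 − 15 = −7.5.
- **(a) 6.2 order, equal regrowth on both arms.** No effect: D = (15q − 15) − (15q − 15) = 0. 50% effect: D = 7.5q − 15q = −7.5q, which is −7.1, −6.75 and −6.0. This is attenuation, with no false signal.
- **(b) 6.2 order, BBL leaving the treated arm hair-free.** No effect: D = 0 − (15q − 15) = 15(1 − q), which is +0.75, +1.5 and +3.0 lesions, against BBL.
- **(c) One-arm shave before measurement at Day 0 (6.1.1), both arms unshaved when measured at Day 51 (6.2.5).** No effect: D = (15q − 15) − (15q − 15q) = −15(1 − q), which is −0.75, −1.5 and −3.0 lesions, in favour of BBL.
- **(d) One-arm shave before measurement at both visits.** No effect: D = (15 − 15) − (15q − 15q) = 0, but the treated side is on view.

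So the direction of any distortion depends on which text is followed and on whether BBL changes hair. An equal additive shift in both arms cancels; an unequal state between arms does not.

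**The case against.** The case for treating this as a minor wording matter has force.

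- **6.1.1 is not a sequence.** It lists the coordinator's check before departure ahead of the BBL treatment itself, so its bullets do not prove that a one-arm shave precedes the pictures. The 6.2 lists are unnumbered too. This stands: the order is listed, not expressly mandated.
- **The visit-level text is bilateral.** A reader might infer from 6.1.1 that every picture shows the assignment, or that the plan as a whole reveals treatment. The documents do not support either. Day 51 has no treatment, and 6.2.5 shaves both arms there. Under 3.1 and 6.2, shaving gives no cue at any visit. The unmasking is conditional on 6.1.1 being followed.
- **Follow-up measurement precedes that day's shave as listed.** That day's shave could not then unmask the evaluator. This also stands. The remaining cue at Day 51 would come from hair reduction.
- **The endpoint is a between-arm contrast.** A reader might infer that different conditions at Day 0 and Day 51 bias it in themselves. Case (a) shows that they do not when regrowth is equal and there is no effect.
- **Nothing says that hair hides lesions.** Eligibility requires ecchymosis above 1 cm on each arm, and no section says that forearm hair impairs measurement. The values of q are assumptions.
- **Measuring before shaving can be defended.** The background describes vessels that tear with trivial trauma, and skin tears are a secondary endpoint, so a shave just before the count could add marks. This bears on which order to choose, not on whether the order should be the same at each visit.

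What survives is the contradiction in 6.1.1, the unequal listed order at the two ends of the primary change, and the possibility that hair differs by arm at Day 51.

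**Conclusion.** The concern holds in a limited form. Section 6.1.1 conflicts with 3.1, 6.2.2, 6.2.3 and 6.2.5 on which arm is shaved, and following it would identify the treated side to later viewers, against 8.5. As listed, the evaluator's two primary readings are taken on differently prepared skin. The photographs do not share that second problem.

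The size cannot be derived from the documents. Under the assumed 15 lesions per arm and 80% to 95% visibility on unshaved skin, the spurious difference runs from 0 to 3 lesions and may favour either side. The larger values require unequal hair between the arms, either from BBL itself or from mixing 6.1.1 at Day 0 with 6.2.5 at Day 51. The précis plans only 5 older subjects with purpura, so inconsistent handling of one or two could matter.

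This is worth correcting because the protection is nearly free. It is not evidence that the trial's masking fails under the plan as a whole.

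**What to change.** 1. Reconcile 6.1.1 with 3.1 and 6.2 so that both lower arms are handled identically at every visit.
2. State one explicit order of shaving, pictures and evaluator measurement, the same for both arms at Days 0, 7, 14, 21 and 51, and say that it is a required sequence.
3. In choosing the order, note that measuring after both arms are shaved would equalise hair between arms and between Day 0 and Day 51, provided that shaving is finished before the evaluator sees the arms. Measuring first at every visit would match the order but not the hair: Day 0 would be on hair not yet shaved for the study and Day 51 on about 30 days of regrowth, possibly unequal by arm.
4. If measurement follows shaving, add a rule that a mark or tear caused by that day's shave is not counted as a lesion or skin tear on either arm.

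The cost is protocol wording and a reordering of steps already listed, with no added visit or equipment. The small downside is the rule in item 4, which matters more in fragile skin. The change would not hide other listed BBL effects, such as fewer lentigines or altered pigmentation, so it removes one cue to side and not all of them.

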- 2. Mean absolute difference in the number of skin tears at baseline and 30 days after the last treatment
- 3. The changes in collagen and elastin between untreated and treated skin
- 4. Mean absolute difference in the change in epidermal thickness between treated and untreated skin
- 5. Changes in gene expression between treated and untreated skin

Population: Sample size 10

Male and female adults over the age of 21 living in Palm Beach

County Florida.

Number of Sites 1

Study Agent: Sciton's BBL

Study Duration: 51 days

SCHEMATIC OF STUDY DESIGN

Day -30 to 0 Screening

- •Total n=10
- Obtain informed consent
- Screen potential subjects by inclusion and exclusion criteria (Eligibility Questionnaire)

Day 0: Randomization

•Subjects randomized to have BBL on either their left or right

Day 0: Baseline assessments/ Study Intervention

• Baseline Assessments:

Pre-procedure pictures of patient's lower arms taken with a Digital Camera

Baseline assessment and measurement by evaluator

Baseline Medical History and Medication questionnaires completed by all subjects

• Study Intervention #1:

Sciton's BBL done according to purpura protocol on one arm according to randomized assignment

• Post-Procedure Assessments:

Post-procedure questionnaires filled out by all subjects

Day 1: Follow-up assessments

• At Home Follow-up Assessments Questionnaire Regarding Side-Effects

Day 2: Follow-up assessments

• At Home Follow-up Assessments Questionnaire Regarding Side-Effects

Day 7 +/- 2 Days: Follow-up assessments / Study Intervention

Follow-up assessments:

Evaluator assessment and measurement

Pictures taken of subject's lower arms

Subject follow up questionnaires filled out by all subjects

• Study Intervention #2:

Sciton's BBL done a second time on the assigned arm according to protocol settings

• Post-Procedure Assessments:

Day 14 +/- 2 Days: Follow-up assessments / Study Intervention

• Follow-up assessments:

Evaluator assessment and measurement Pictures taken of subject's lower arms

Subject follow up questionnaires filled out by all subjects

• Study Intervention #3:

Sciton's BBL done a third time on the assigned arm according to protocol settings

• Post-Procedure Assessments:

Post-procedure questionnaires filled out by all subjects immediately after treatment

Day 21 +/- 2 Days: Follow-up assessments / Study Intervention

• Follow-up assessments:

Evaluator assessment and measurement

Pictures taken of subject's lower arms

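### The treatment 2 settings rule ignores non-blistering reactions after Day 2, gives no setting for mixed NONE and MINIMAL answers, and states no precedence after a late blister

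*Combined protocol and SAP*

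**What the plan says.** Protocol 6.1.1 fixes the first treatment at 10 Step 1 passes, 10 J in Step 3 and 8 J in Step 4. Treatment 2 then has four branches:

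- Lower Steps 3 and 4 by 2 J: "If any answers on the post procedure side effects questionnaire from day 0,1, or 2 were SEVERE or if the patient had blisters".
- Lower them by 1 J: "If any answers on the post procedure side effects questionnaire on day 0,1, or 2 were MODERATE with NO blistering".
- Keep the settings: "If all answers on the post procedure side effects questionnaire on day 0,1, or 2 protocol were MINIMAL".
- Add 10 Step 1 passes and 1 J in Steps 3 and 4: "If all answers on the post procedure side effects questionnaire on day 0,1, or 2 protocol were NONE".

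For treatments 3 and 4 the day limit is gone and the keep branch is worded differently: "If any answers on the post procedure side effect questionnaire were MINIMAL with NO blistering".

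Treatment 2 is scheduled at Day 7, plus or minus 2 days (6.2.3). Section 3.1 states: "Side effects will be measured on Day 0, 1, 2, 7, 14, 21, 22 and 51". The schematic lists, for the Day 7 visit and ahead of the intervention, "Subject follow up questionnaires filled out by all subjects". Section 6.2.3 also places adverse event recording and an eligibility review before BBL at that visit.

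**The concern.** The rule sets how much energy the treated arm receives, and 2.3.1 lists severe burn, ulceration and scarring among the rare risks. A rule of this kind should use what is known when the settings are chosen, and should give exactly one answer for each course a subject can have. The treatment 2 text falls short in three ways:

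1. Apart from blisters, nothing seen after Day 2 counts.
2. The two mildest branches both require all answers to be the same.
3. Neither of those two branches excludes blisters, and no order of precedence is given.

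The safety of this BBL regimen is itself a secondary objective, so an unclear rule also leaves the tested regimen partly undefined.

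**Working it through.** The documents give no figure to reproduce; this is a check of rule logic. Settings are written as Step 1 passes / Step 3 J / Step 4 J, all from 6.1.1.

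| Branch at treatment 2 | Setting |
|---|---|
| A: any SEVERE (Days 0-2) or any blister | 10/8/6 |
| B: any MODERATE (Days 0-2), no blister | 10/9/7 |
| C: all MINIMAL (Days 0-2) | 10/10/8 |
| D: all NONE (Days 0-2) | 20/11/9 |

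**Late non-blistering reaction.** Treatment 2 falls between Day 7 - 2 = Day 5 and Day 7 + 2 = Day 9, so 3 to 7 days pass after the last day the questionnaire triggers use. If all answers to Day 2 are NONE and a non-blistering reaction then appears, A, B and C are not met and D is. The setting goes from 10/10/8 to 20/11/9: 10 more passes, 1/10 = 10% more energy in Step 3 and 1/8 = 12.5% more in Step 4. If the same reaction were graded SEVERE by Day 2, the setting would be 10/8/6.

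**Mixed NONE and MINIMAL.** An example is slight redness on Day 0 that is gone by Day 2. A and B are not met; C and D fail because each needs all answers alike. With one question on three days there are 2^3 = 8 NONE/MINIMAL patterns, of which only the two uniform ones meet a branch, so 6 of 8 meet none. At treatments 3 and 4, where one MINIMAL answer is enough, 0 of 8 are left out.

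**Late blister.** The blister trigger in A has no day limit, and C and D have no blister condition.

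- All NONE, then a blister: A gives 10/8/6 and D gives 20/11/9, a difference of 3 J in each of Steps 3 and 4.
- All MINIMAL, then a blister: A gives 10/8/6 and C gives 10/10/8.

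**Full enumeration for treatment 2.** Four grades give 15 non-empty sets of answers; with and without a blister that is 30 states. One state (NONE with MINIMAL, no blister) meets no branch, 23 meet one and 6 meet two. All six double matches include A, so reading the branches worst-first settles them. It settles neither the gap nor the Day 2 cut-off.

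**Treatments 3 and 4.** There is no day limit, but the trigger is the post-procedure questionnaire. The schematic describes that form, at Days 14 and 21, as completed straight after treatment, and lists the follow-up questionnaire separately. If only the post-procedure form counts, later non-blistering reactions may be missed here too. If later forms count, they are not.

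**The case against.** The strongest reply is that a clinician would apply the rule sensibly. The branches run from worst to best, blisters are an explicit trigger in the first, and the wording for treatments 3 and 4 shows that a NONE/MINIMAL mix should keep its settings. Most of this stands. Under worst-first every double match disappears, including those from SEVERE and MODERATE answers together. A reader might infer from the overlaps that the rule is mostly unworkable; the documents do not support that, since the overlaps depend on refusing the ordinary reading.

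The count of 6 in 8 also depends on a reading. If the day phrase means all answers on any one of the days, then with one question every pattern meets a branch, and the six mixed ones meet both C and D. A subject with mixed answers on each of the three days would still meet none. The ambiguity remains, but the count is not fixed.

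A reader might further infer that a severe late reaction would routinely be followed by more energy. That goes too far. The Day 7 forms are not in the documents and may not use the same grades. The course also requires no side effect at all through Day 2. Other provisions could intervene:

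- the pre-BBL eligibility review (6.2.3), with newly developed exclusion criteria or declining health as grounds for termination (4.4.1);
- suspension of the study for unacceptable risk (4.5);
- notification of any adverse event to the IRB within 24 hours (7.4.1);
- the medical monitor (7.6);
- the Statement of Compliance, which permits departures to remove an immediate danger.

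These are real but partial safeguards. They are largely discretionary, do not clearly cover isolated pain or erythema, and none sets a dose.

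**Conclusion.** The concern holds as a defect in the wording of a dosing rule. On the plain text, treatment 2 can be raised to 20/11/9 after a non-blistering reaction that began after Day 2, an ordinary mild course has no stated setting, and a late blister meets two branches unless worst-first is supplied by the reader.

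The Day 2 cut-off is in the text and needs no assumption. The mixed-answer gap rests on pooling all answers over Days 0 to 2. Whether treatments 3 and 4 share the late-reaction problem depends on which form is meant, so a reader should not infer that they are free of it. The counts are of patterns, not probabilities, and the documents give no frequency for late reactions. Nor should a reader infer any bias in the efficacy result: the primary comparison of the two arms is unaffected. This is a cheap improvement for patient safety.

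**What to change.** Replace the treatment 2 branches and the treatment 3 and 4 branches in 6.1.1 with one rule. Base it on all side-effect findings since the previous treatment, including the assessment at the treatment visit before BBL, and state that the worst finding governs:

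1. Any SEVERE finding or any blister: reduce Steps 3 and 4 by 2 J.
2. Otherwise any MODERATE: reduce Steps 3 and 4 by 1 J.
3. Otherwise any MINIMAL: same settings as the previous visit.
4. Otherwise (all NONE and no blister): add 10 Step 1 passes and 1 J in each of Steps 3 and 4.

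Every combination of grades and blisters then meets exactly one line. Name the forms that feed the rule and confirm that the visit-day form uses the same NONE to SEVERE grades. The treating investigator and the coordinator, who already know the assigned arm (8.5), can review the forms before choosing the settings, so the evaluator's blinding is not touched.

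The cost is a few lines of text and a short form review before treatments 2, 3 and 4; the visit-day assessments are already scheduled. The downside is that possibly fewer subjects reach the higher settings.
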